9.1.2. Active Disease and Late Relapse Population (Group 2)

A total of approximately 60 Group 2 patients are planned to be enrolled and treated with MT-401, 30 patients in Subgroup C (frank relapse patients) and 30 patients in Subgroup D (MRD $^+$). After approximately the first 10 patients in each subgroup have progressed or have had the opportunity to be followed for 6 months, clinical safety and efficacy will be reviewed comprehensively. Patients who develop CR_{MRD} after bridging therapy and patients who relapse early (defined < 90 days \pm 10 days post-transplant and termed Group 2 Early Relapse patients) will be analyzed separately, and not be counted as part of the 60 patients in Group 2.

Overall response rates in the literature vary widely and range from 10% to 60% (Loren and Porter, 2008; Porter et al, 2010). Complete remission rates would be expected to be lower than ORR rates. The sample size of 30 per subgroup is not based on a formal power calculation. An increase in the CR rate of greater than 10-15% compared to historical rates for standard of care would be considered clinically meaningful.

If the decision is made to dose patients in Phase 2 with any of the MT-401 dosing regimens evaluated in Cohorts III-V, enrollment will continue in Phase 2 Group 2 to achieve 60 evaluable patients treated with the final MT-401 dose and manufacturing process, thereby replacing any patients that have not been treated with the final Phase 2 product as determined by the Sponsor.

For historical control response rates ranging from 5% to 40%, the observed treatment effects (and associated 95% confidence intervals) needed to attain 80% and 90% power with a sample size of 30 patients per subgroup are provided in Table 7.

Confidential Page 50 of 74

Table 7. Power^a and 95% Confidence Intervals Relative to Historical Control Rates

Historical Control CR Rate	Observed Treatment Effect (80% Power) (95% CI)	Observed Treatment Effect (90% Power) (95% CI)
5%	21% (9%, 40%)	25% (11%, 44%)
10%	29% (14%, 48%)	32% (17%, 52%)
15%	36% (19%, 55%)	40% (22%, 59%)
20%	43% (25%, 62%)	47% (28%, 66%)
25%	50% (31%, 68%)	53% (34%, 72%)
30%	53% (34%, 71%)	57% (37%, 75%)
35%	60% (40%, 77%)	63% (44%, 80%)
40%	63% (43%, 79%)	66% (47%, 82%)

^a based on a 1-sided exact test at the 0.05 alpha level.

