The primary endpoint of RFS for Group 1 will be tested at $\alpha = 0.05$ (two-sided) at the final analysis. The analysis of RFS at the interim analysis will be performed for the purposes of testing for futility and possible re-estimation of sample size as described in [Section 7.4.7.3](#). Analysis at the interim and final analysis will be performed based on ([Chen et al. 2004](#)) in order to maintain the type 1 error at $\alpha = 0.05$ for RFS at the final analysis.

Secondary endpoints for Group 1, OS and GRFS, will be presented for descriptive purposes only and no adjustments will be made for multiplicity.

The primary endpoint of CR for Group 2 will be tested at $\alpha = 0.05$ (two-sided) at the final analysis. DOCR will be presented for descriptive purposes only and no adjustments will be made for multiplicity.

7.4.7.6 *Use of an “Efficacy Subset” of Patients*

The primary efficacy analysis for Group 1 will be performed on all randomized patients and the PP population will be utilized as a sensitivity analysis. The PP population will exclude patients received less than two-thirds of total planned dose or had other major protocol deviations.

7.4.7.7 *Examination of Subgroups*

Subgroup analyses may be conducted based on, but not limited to, the covariates defined in [Section 7.4.7.1](#).

For time to event endpoints forest plots of the event-free rates at landmark times may be generated to display the outcomes in subgroups. Additionally, Kaplan-Meier plots with subgroup KM curves overlaid on the same plot may be presented. For binary endpoints, the rates within subgroups may be presented in forest plots.

7.5 **Safety Evaluation**

Safety analysis will be carried out for the all treated patients population, to include all patients who receive at least one dose of study drug. Patients who do not complete the study, for whatever reason, will have all available data up until the time of termination included in the analysis. For safety analysis presented by study visit, the baseline value will be defined as the last value reported prior to first study drug administration.

7.5.1 *Extent of Exposure*

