If the decision is made to dose patients in Phase 2 with any of the MT-401 dosing regimens evaluated in Cohorts III-V, enrollment will continue in Phase 2 Group 2 to achieve 60 evaluable patients treated with the final MT-401 dose and manufacturing process, thereby replacing any patients that have not been treated with the final Phase 2 product as determined by the Sponsor.

For historical control response rates ranging from 5% to 40%, the observed treatment effects (and associated 95% confidence intervals) needed to attain 80% and 90% power with a sample size of 30 per subgroup are provided in [Table 3](#).

Table 3. Power^a and 95% Confidence Intervals Relative to Historical Control Rates

Historical Control CR Rate	Observed Treatment Effect (80% Power) (95% CI)	Observed Treatment Effect (90% Power) (95% CI)
5%	21% (9%, 40%)	25% (11%, 44%)
10%	29% (14%, 48%)	32% (17%, 52%)
15%	36% (19%, 55%)	40% (22%, 59%)
20%	43% (25%, 62%)	47% (28%, 66%)
25%	50% (31%, 68%)	53% (34%, 72%)
30%	53% (34%, 71%)	57% (37%, 75%)
35%	60% (40%, 77%)	63% (44%, 80%)
40%	63% (43%, 79%)	66% (47%, 82%)

^a based on a 1-sided exact test at the 0.05 alpha level.

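### Protocol Table 7 and SAP Table 3 present assumed true CR rates as the observed rates needed; the observed counts that reject are lower, and the printed power does not match the SAP's two-sided test

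*Protocol*

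**What the plan says.** Protocol 9.1.2 plans "30 patients in Subgroup C (frank relapse patients) and 30 patients in Subgroup D" and states that "The sample size of 30 per subgroup is not based on a formal power calculation". It then introduces Table 7, whose rows are historical CR rates between 5% and 40%, as giving "the observed treatment effects (and associated 95% confidence intervals) needed to attain 80% and 90% power with a sample size of 30 patients per" Group 2 subgroup. The column heads follow the same wording: "Observed Treatment Effect (80% Power) (95% CI"). The footnote says the figures are "based on a 1-sided exact test at the 0.05 alpha level".

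SAP 7.6 repeats the table as Table 3, with the same rates, intervals and footnote, and the same introduction: "the observed treatment effects (and associated 95% confidence intervals) needed to attain 80% and 90% power with a sample size of" 30 per subgroup.

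SAP 7.4.7.5 specifies a different test from the footnote: "The primary endpoint of CR for Group 2 will be tested at" a two-sided 0.05 level at the final analysis. SAP 7.1.1 also makes two-sided testing at 0.05 the general rule. Neither document fixes a single historical rate for that test or lists a critical count.

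**The concern.** Power is the probability of rejecting when the true rate takes a given value. An observed rate either rejects or does not; it does not attain a power. The sentence and column heads therefore name the wrong quantity, and the attached 95% intervals make the entries look like trial results.

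CR rate is a primary endpoint of Group 2. This table is the only place in either document that ties a CR rate to a historical rate, a test and a power. Someone who takes the heading literally would set the bar for a positive subgroup above the point where the test rejects. The footnote's one-sided 0.05 test is also more lenient than the test in SAP 7.4.7.5, so the stated 80% and 90% do not describe the analysis the SAP specifies.

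**Working it through.** **Inputs.** n = 30 per subgroup, historical rates p0 of 5% to 40% in steps of 5 points, and the one-sided exact test at 0.05 (all from Protocol 9.1.2 and the Table 7 footnote). The two-sided 0.05 test comes from SAP 7.4.7.5; I take it as 0.025 in the upper tail, which agrees with excluding p0 by an exact (Clopper-Pearson) 95% CI.

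**Formulas.** With X binomial(30, p):
- critical count r = smallest r with P(X ≥ r | p0) ≤ α;
- power at true rate p = P(X ≥ r | p);
- count needed to observe at least a printed rate, k = 30 × printed rate, rounded up;
- chance of reaching the printed rate when it is true = P(X ≥ k | printed rate).

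**Step 1: reproduce the table, using the 20% row.** P(X ≥ 10 | 0.20) = 0.0611 and P(X ≥ 11 | 0.20) = 0.0256, so r = 11 at one-sided 0.05. Solving P(X ≥ 11 | p) = 0.80 gives p = 42.6% (printed 43%), and 0.90 gives 46.6% (printed 47%). The exact CI at the fractional count 30 × 0.4263 = 12.8 is 24.9% to 61.9% (printed 25%, 62%).

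**Step 2: all rows.** Solved true rates against printed rates:

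| p0 | 80% power: solved / printed | 90% power: solved / printed |
|---|---|---|
| 5% | 21.4 / 21 | 24.9 / 25 |
| 10% | 28.7 / 29 | 32.5 / 32 |
| 15% | 35.7 / 36 | 39.7 / 40 |
| 20% | 42.6 / 43 | 46.6 / 47 |
| 25% | 49.4 / 50 | 53.3 / 53 |
| 30% | 52.7 / 53 | 56.6 / 57 |
| 35% | 59.2 / 60 | 63.0 / 63 |
| 40% | 62.4 / 63 | 66.2 / 66 |

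All 16 cells agree within one point. Under the footnote's test, power at the printed rates is 78.5-82.5% (80% column) and 89.0-90.7% (90% column).

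**Step 3: the entries are not observed results.** All 16 printed intervals match the exact interval at 30 times the unrounded true rate. The two 53% cells carry different intervals, (34%, 72%) and (34%, 71%), which one observed count cannot do. The 50% cell is printed with (31%, 68%), while 15/30 observed gives 31.3% to 68.7%. No count out of 30 rounds to 21% or 29%.

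**Step 4: what an observed result must reach, and the power at the printed 80%-column rate.**

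| p0 | r, one-sided 0.05 | r, 0.025 per tail | Power at printed rate, one-sided 0.05 | Power at printed rate, 0.025 per tail | k to reach printed rate | Chance of reaching it if true |
|---|---|---|---|---|---|---|
| 5% | 5 | 5 | 78.5% | 78.5% | 7 | 44.7% |
| 10% | 7 | 8 | 81.0% | 67.7% | 9 | 52.1% |
| 15% | 9 | 10 | 80.8% | 68.4% | 11 | 53.8% |
| 20% | 11 | 12 | 81.1% | 69.5% | 13 | 55.5% |
| 25% | 13 | 13 | 81.9% | 81.9% | 15 | 57.2% |
| 30% | 14 | 15 | 81.0% | 69.6% | 16 | 55.9% |
| 35% | 16 | 17 | 82.5% | 71.5% | 18 | 57.8% |
| 40% | 17 | 18 | 81.9% | 70.6% | 19 | 56.6% |

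Under the footnote's test the rejecting count is two below k in every row. At 0.025 per tail the gap is one responder in six rows and two in the 5% and 25% rows.

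**The case against.** Much of the case on the other side stands. The arithmetic in the table is right; only the label is wrong. The *(80% Power)* heads and the footnote let a statistician work out what was meant. The sample size is expressly not a power calculation, so it is not undermined.

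Three stronger readings are tempting, and the documents do not support them.

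- *The plan loses power.* No section makes the table a decision rule. The Group 2 objective is to estimate the CR rate, the analysis is the rate with an exact 95% CI (Protocol 9.3.3, SAP 7.4.4), and the interim review rests on the totality of the data (Protocol 9.5.2, SAP 7.4.7.3). The 45-58% figures apply only to a reader who uses the printed rates as observed thresholds. They also read a printed rate as at least this rate: in the 5% row, 21% of 30 is 6.3, and rounding down to 6 would give 62.5%.
- *The table is the only yardstick for Group 2.* Protocol 9.1.2 also calls a CR increase above 10-15% over historical rates clinically meaningful. Protocol 9.3.3 sets Subgroup C beside a retrospective study, and the SAP allows a synthetic control arm under a separate plan.
- *A result such as 11/30 beats a 20% historical rate but would be called short of 43%.* That holds only under the footnote's test. The one-sided p-value is 0.0256, above 0.025, and the exact 95% CI of 19.9% to 56.1% includes 20%. The SAP's test needs 12/30.

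The mislabelling survives these limits: under either test the rejecting count is below the printed rate in every row.

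**Conclusion.** The point holds as a labelling error in both documents, together with a mismatch between the table's test and the SAP's. The label overstates the observed count needed by two responders per row under the footnote's test, and by one or two under the SAP's. Separately from the label, the nominal 80% becomes about 68-72% in six of eight rows once the SAP's two-sided test is used; the 5% and 25% rows are unchanged because their critical counts are the same. These figures assume n = 30 exactly, a fixed historical rate, and 0.025 in the upper tail for the two-sided test. The error is worth correcting because a primary endpoint that the SAP says will be tested has no other stated link between rate, test and power. It does not call the sample size or the planned estimation into question.

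**What to change.** In Protocol 9.1.2 (Table 7) and SAP 7.6 (Table 3):

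1. Rename the columns *Assumed true CR rate giving 80% (90%) power*, and correct the sentence above the table to match.
2. Recompute the table for the test in SAP 7.4.7.5, or reconcile the sidedness between that section and the footnote. At 0.025 per tail, the true rates for 80% power are 21.4, 32.2, 39.2, 46.0, 49.4, 55.9, 62.4 and 65.6%.
3. Drop the intervals now attached to the true rates.
4. Add a column for the minimum observed CRs of 30 that reject each historical rate, with the exact 95% CI. At 0.025 per tail it would read: 5 (5.6-34.7%), 8 (12.3-45.9%), 10 (17.3-52.8%), 12 (22.7-59.4%), 13 (25.5-62.6%), 15 (31.3-68.7%), 17 (37.4-74.5%) and 18 (40.6-77.3%). Each lower limit lies above its historical rate.

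The cost is one revised table and one sentence in each document. Enrolment, assessments and sample size do not change.

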9.1.3. Safety Lead-in (Cohorts I and II) and Cohorts III-V

Approximately 6-12 patients are expected to be treated in the Safety Lead-in portion of this study per a standard 3+3 design with 2 planned cohorts. In addition, approximately 9-18 patients (3-6 patients per cohort) are expected to be treated in the Cohorts III-V portion of this study as per a standard 3+3 design.

9.2. Populations for Analyses

Populations for analyses are defined in Table 8.

Table 8. Populations for Analysis

Population	Description
All enrolled patients	All patients who sign the ICF and donor undergoes leukapheresis
All randomized patients in Phase 2 (Adjuvant - Group 1 only)	All patients in Group 1 who are randomized with final dose and manufacturing process, and are MRD prior to randomization by central testing and local testing (if a local test was a lso performed). Efficacy analyses for Group 1 will be conducted in this population. A patient randomized based on negative MRD result per central test but confirmed to be MRD will be excluded from Group 1 analyses. The patient will
All treated patients	be included in Group 2 Subgroup D analyses if treated with MT-401. All patients who receive at least one dose of MT-401 or were randomized to SoC. Patients whose product includes fewer cells or does not meet specifications may still be treated, but will be summarized separately from patients whose product meets specifications. For - Group 1, safety analyses will be conducted in this population, and safety data for patients randomized to SoC will also be shown for reference. For - Group 2, all efficacy analyses and safety analyses will be conducted in this population. For the Safety Lead-in (Cohorts I and II) and Cohorts III-V, all efficacy and safety analyses will be conducted in this population.
DLT-eva luable	All patients in the Safety Lead-in (Cohorts I and II) and Cohorts III-V who receive at least one dose of MT-401 and have had the opportunity to be followed for 28 days from the initial MT-401 infusion or have experienced a DLT.
Per-protocol in Phase 2	All treated patients, as defined above, who have no major protocol deviations. Select efficacy analyses for Group 1 and Group 2 will be conducted in this population for sensitivity analysis.

Confidential Page 51 of 74

Abbreviations: DLT=dose-limiting toxicity; ICF=informed consent form; MRD=minimal residual disease; SoC=standard of care

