7.2 Analysis Populations

The analysis populations are defined as follows:

- All Treated Patients: Includes all patients who received at least one dose of MT-401 or were randomized to SOC.
- All Randomized Patients: Includes all patients in Group 1 who were randomized with final dose and manufacturing process and are MRD⁻ prior to randomization by central testing and local testing, if a local test was also performed. A patient randomized based on negative MRD result per central test but confirmed to be MRD⁺ will be excluded from Group 1 analysis.

When MRD testing occurs with different methodology (eg, flow cytometry and PCR), the patient is considered MRD⁺ if either test detects MRD. If adjudication occurs between central testing and local testing for the same type of testing (eg, flow by central testing and flow by local testing), the final adjudicated result will be taken into account for the confirmed MRD result. A patient confirmed to be MRD⁺ prior to randomization will be excluded from Group 1 and will be included in Group 2 analysis if treated with MT-401.

- Per-Protocol (PP) Population: Includes all treated patients, as defined above, who have no major protocol deviations. If there is <5% difference in the all randomized patient population and the PP population for Group 1, no analyses will be performed on the PP population.

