7.4 Efficacy Evaluation

7.4.1 *Datasets Analyzed*

Efficacy analyses for Group 1 will be conducted in the all randomized patients population while efficacy analyses for Cohorts I-V and Group 2 will be conducted in the all treated patients population. Select efficacy analyses for Group 1 will be repeated in the PP population. A data listing of patients excluded from the PP Population, to include the reason for exclusion, will be presented.

7.4.2 *Demographic and Other Baseline Characteristics*

Demographic and baseline characteristics will include: age, sex, ethnicity, race, height, weight, and body mass index (BMI). Age will be calculated relative to date of informed consent, as follows:

- If the month and day portion of the informed consent date is prior to the month and day portion of the birthdate, age will be calculated as the year of informed consent minus the year of birth, minus one;
- If the month and day portion of the informed consent date is on or after the month and day portion of the birthdate, age will be calculated as the year of informed consent minus the year of birth.

BMI will be calculated as: weight (kg) / [height (cm) / 100]². Age, height, weight, and BMI will be summarized using descriptive statistics. Sex, age category (18-64 years, 65 years and above), ethnicity, and race will be summarized with the number and percentage of patients in each parameter category.

Disease history characteristics include: time since initial diagnosis (months), WHO classification, type of AML (secondary or treatment-related AML, de novo AML), disease status at screening, disease status at baseline, bone marrow blast percentage at baseline (for Cohort I-V and Group 2) complete remission prior to transplant (CR1/CR2/CR3; for Group 1 only), prior stem cell transplant (yes/no), time from transplant to randomization/first dose, time from first post-transplant relapse to first dose (for Cohort I-V and Group 2), history of post-transplant chronic GVHD (yes/no), maximum grade of chronic GVHD, history of post-transplant acute GVHD (yes/no), maximum grade of acute GVHD, type of transplant donor, conditioning regimen, MRD status pre- and post-transplant, genetic mutations identified, disease risk classification (favorable,

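### The Group 2 efficacy set does not carry the final-product restriction that the replacement rule implies

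*Protocol*

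**What the plan says.** Phase 2 opens at one dose with the initial manufacturing process. The Sponsor may change the dose after Cohort III, and may move to the accelerated process after Cohorts IV and V (Protocol 4.3.2; SAP 6.3.1). For Group 2, Protocol 9.1.2 says that in this event "enrollment will continue in Phase 2 Group 2 to achieve 60 evaluable patients treated with the final MT-401 dose and manufacturing process". Those already treated under another regimen are to be replaced, and the Sponsor decides who they are. SAP 7.6 repeats the rule.

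The analysis sets are defined elsewhere. Protocol Table 8 (Section 9.2) defines All Treated as "All patients who receive at least one dose of MT-401 or were randomized to SoC" and states that for Group 2 "all efficacy analyses and safety analyses will be conducted in this population". SAP 7.2 gives the same definition: "Includes all patients who received at least one dose of MT-401 or were randomized to SOC". SAP 7.4.1 adds that "efficacy analyses for Cohorts I-V and Group 2 will be conducted in the all treated patients population".

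For Group 1, Table 8 restricts the efficacy set: "All patients in Group 1 who are randomized with final dose and manufacturing process". SAP 7.2 has the same limit.

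**The concern.** The replacement rule and the analysis set answer the same question differently. The rule treats a Group 2 patient on a superseded regimen as not counting toward the target. The set keeps that patient in the numerator and denominator of the CR rate and, if in remission, in DOCR. The patients at issue were dosed correctly under the Phase 2 regimen then in force. They are not patients with a short or failed product.

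At stake is what the primary Group 2 estimate describes. If the sets are followed literally after a change, it is a mixture over two regimens, with weights set by how many patients happened to be treated before the change. If they are not followed literally, the choice between pooled and final-product rates is open. Group 2 is unblinded and single-arm, the Sponsor reviews its efficacy after about 10 patients per subgroup (Protocol 4.1; SAP 6.1), and the Sponsor also determines which product is final. That choice should be settled on paper beforehand.

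**Working it through.** **1. The clauses side by side**

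| | Group 1 | Group 2 |
|---|---|---|
| Enrolment target after a change | 150 evaluable randomized, about 75 treated with the final product | 60 evaluable on the final product |
| Efficacy set | Randomized with final dose and process | At least one dose of any MT-401 |
| Final-product limit in the set | Yes | No |

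**2. Does another clause remove the earlier Group 2 patients?**

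- *Separate summary in Table 8:* "Patients whose product includes fewer cells or does not meet specifications may still be treated, but will be summarized separately". This covers low-cell or out-of-specification product, not an in-specification product made under an earlier regimen. SAP 7.2 omits it.
- *Protocol Table 5 footnote c and Section 6.6:* these concern individual departures from the intended dose, mainly from manufacturing limits. They also disagree on whether such patients are unevaluable or evaluable in a separate subgroup, and should be reconciled.
- *Per-protocol set:* this removes major deviations. Following the regimen in force is not a deviation.
- *SAP 7.1.1:* Group 2 outputs are presented by treatment actually received. That could allow a split by regimen, but for CR the only split specified is Subgroup C versus D (SAP 7.4.4).
- *Protocol 9.1.2 itself:* it says that patients in MRD-negative CR after bridging, and early-relapse patients, are analysed separately and not counted in the 60. It says only that superseded-regimen patients are replaced.

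No clause takes them out, and evaluable is never turned into a Group 2 analysis set.

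**3. Reproducing the plan's own figure (Protocol Table 7, SAP Table 3)**

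Inputs are n = 30 per subgroup and a one-sided exact binomial test at 0.05. In the row for a 20% historical rate:

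- The smallest r with P(X ≥ r | 30, 0.20) ≤ 0.05 is r = 11, with tail probability 0.0256.
- Solving P(X ≥ 11 | 30, p) = 0.80 gives p = 42.6%. The table states 43%, where power is 81%.

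The other rows agree to within rounding. The table therefore describes 30 patients per subgroup, the number planned on the final product.

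**4. What pooling does**

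Let m be the number of earlier-regimen patients in a subgroup, s their true CR rate, and p the final-product rate.

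Expected pooled rate = (30p + m·s) / (30 + m), so the shift from p is [m / (30 + m)] × (s − p).

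The documents give neither m nor s. Both are assumptions here, and p = 43% is taken from Table 7.

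With m = 10:

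| s | Calculation | Pooled rate |
|---|---|---|
| 10% | (12.9 + 1.0)/40 | 35% |
| 20% (historical rate) | (12.9 + 2.0)/40 | 37% |
| 31.5% (halfway between 20% and 43%) | (12.9 + 3.15)/40 | 40% |

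At m = 10 the shift is one quarter of (s − p), so it is upward whenever s exceeds 43%.

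With s = 20% and m varied:

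- m = 5: 13.9/35 = 39.7%
- m = 15: 15.9/45 = 35.3%
- m = 30: 18.9/60 = 31.5%

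As observed counts with exact 95% intervals: 13/30 = 43.3% (25.5 to 62.6) on the final product alone becomes 15/40 = 37.5% (22.7 to 54.2) after adding 2 responders among 10 earlier patients.

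**The case against.** The strongest reply is that the intent is plain. The replacement rule appears in the overall design and sample-size sections of both documents, and replaced patients ordinarily leave the evaluable count. The interim provisions (Protocol 9.5.2; SAP 7.4.7.3) point the same way: Cohort IV and V patients may join Group 2 analyses only if they had the same manufacturing process. A reader might infer that the sponsor means to pool regimens, or that replacement serves no purpose. The documents support neither. Final product only is the likelier intent, and replacement would still secure 30 final-product patients per subgroup. What remains is that neither set definition states this intent.

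The problem is also conditional. The Sponsor may keep the current regimen. If it does, or if no Group 2 patient is treated before a change, nothing is affected.

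A reader might also infer that the CR rate would be understated or the power lost. That does not follow. With a 20% historical rate and m = 10, power of the pooled test is 79% if s = 20% but 88% if s = 31.5%, against 81% without pooling. Both documents say that 30 per subgroup is not a formal power calculation, so a larger n does not break a powered design.

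Finally, restricting the set has a risk of its own: membership would depend on a Sponsor decision that could follow sight of Group 2 responses. That objection stands, and the fix has to deal with it.

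**Conclusion.** The concern holds as a mismatch between the replacement rule and the Group 2 efficacy set, present in both documents. It takes effect only if the Phase 2 dose or process changes after Group 2 patients have been treated. In that case the sets as written give a pooled primary CR rate and pooled DOCR, and the permissive display rule in SAP 7.1.1 does not prevent it.

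The size and direction cannot be stated from the documents. In the illustration with 10 earlier patients, the expected rate falls by about 3 to 8 points from 43%, depending on an assumed earlier rate of 31.5% down to 10%. It would rise if the earlier product did better. For scale, the protocol calls an increase of more than 10-15% over historical rates clinically meaningful. The finding supports a correction of the definitions, not a claim that the Group 2 result is biased in a known direction or underpowered.

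**What to change.** In Protocol Table 8 and SAP 7.2 and 7.4.1:

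- Define a Group 2 efficacy set: patients whose first MT-401 treatment regimen was the final Phase 2 dose and manufacturing process. Re-dosing under Protocol 6.6 should not confer membership. This fits Protocol 9.3, which limits the primary analysis to the first regimen.
- Use this set for CR, DOCR and the Group 2 secondary efficacy endpoints, and tie the word evaluable in Protocol 9.1.2 and SAP 7.6 to it.
- Require the final regimen to be declared and dated without reference to Group 2 response data.
- Report Group 2 patients treated under a superseded regimen in a separate column, and give the CR rate in all treated Group 2 patients as a sensitivity analysis, so that no treated patient drops out of the report.
- Keep All Treated for safety.

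The cost is wording in two documents, one extra table column, and a smaller n than the pooled set would have.
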